**Table 1: Pilot RCT cohort characteristics (mean $\pm$ SD)**

tDCS	Sham	P-value
------	------	---------

Sample (n)	10	10	
Age (years)	83 ± 10	78 ± 10	0.35
Gender (w; m)	5; 5	6; 4	
4m gait speed (m/s)	0.73±0.17	0.72±0.14	0.96
Trail Making B (sec)	174±36	182±46	0.87
Geriatric Depression Scale (scale 0-12)	3±3	4±2.5	0.47
Mini Mental State Exam	24.1±3.4	25.5±3.3	0. 38

tDCS was delivered by the Starstim-8™ (Neuroelectrics, Corp). tDCS was designed to increase the excitability of the left dIPFC using a *non-personalized* approach: the positive electrode was placed over the F3 region of the 10-20 EEG system and the negative electrode was placed over the contralateral supra-orbital margin. Sham stimulation was designed to deliver smaller currents using the same electrode placement, so as to mimic tDCS-induced cutaneous sensations yet have minimal effect on neuronal excitability. Both interventions were well attended (9.1±0.8 of 10 sessions) and no adverse events were reported. Double-blinding procedures were highly effective: following intervention, the number of correct “guesses” of intervention assignment was no greater than that due to chance for participants, as well as study personnel administering tDCS.

Baseline and follow-up assessments included the proposed dual task paradigm and multiple tests of physical and cognitive function. At baseline, the mean (±SEM) dual task cost to standing balance (i.e., the speed of postural sway) was 50±12%. Excitingly, the real tDCS intervention group, as compared to sham, exhibited markedly reduced dual task costs over the two-week follow-up period. Despite the small sample size, similar effects or trends were observed for the dual task cost to walking speed ( $p=0.04$ ), the TUG test of mobility ( $p=0.09$ ), the Trail Making Test of executive function (TMTb – TMTa;  $p=0.11$ ), the Montreal Cognitive Assessment (MoCA,  $p=0.04$ ), and the Geriatric Depression Scale ( $p=0.10$ ).

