By completing this pilot RCT we have 1) strengthened ongoing collaborations between the PI and all co-investigators in this application, 2) developed state-of-the-art and scalable data management infrastructure, 3) ensured that tDCS interventions are safe, well tolerated, well attended, and can be effectively double-blinded in an older adult population similar to that proposed, and 3) enabled more accurate sample size calculations by providing estimates of inter-subject variance in the primary (and most secondary) outcomes proposed in this study, as well as the effects of tDCS intervention on these outcomes. We therefore have confidence

that we can successfully implement and complete the proposed trial and that tDCS targeting the left dlPFC (one of the proposed tDCS intervention targets) will improve dual task performance and other physical and cognitive outcomes on the causal pathway to falls in older adults.

**The degree to which non-personalized tDCS is “on-target” correlates with dual task improvements, yet varies significantly across participants.** A small subset of the cohort described in the previous section completed structural MRIs at baseline. Six of these participants then completed the non-personalized tDCS intervention designed to increase excitability of the left dlPFC. We used the *Stimweaver* framework to model the tDCS-induced electrical field within each participant’s brain. The normal component of this field (believed to facilitate neuronal excitability) within the left dlPFC correlated closely with reductions (i.e., improvements) in the dual task costs to gait speed. However, this normal component varied considerably across participants. These pilot data give us further confidence that 1) the left dlPFC is an important target for dual task performance, and 2) personalizing tDCS to each individual’s head and brain anatomy will likely maximize its effectiveness and reduce inter-subject variability.

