#### Overall approach:

Exploratory analyses will be used to assess outcomes distributions, and any necessary transformations (e.g. to combat significant skew) will be performed prior to estimation of mean treatment effects. Said estimation will use **mixed effects linear regression** of post-intervention outcomes immediately following intervention and at three and six months, with random intercepts and slopes to account for serial correlation in repeated measurements on individuals; models will control for baseline outcomes as in analysis of covariance. Owing to the potential for nonlinear trends in outcomes with time, we will assume no functional form of temporal trends. Missing data will be accommodated by multiple (at least 50) imputation of missing records using algorithms to accommodate the clustered nature of the longitudinal design. Analyses will adjust for the stratified design effect (i.e. control for sex). All estimates will be accompanied by 95% confidence intervals (CIs) for the purposes of reporting in publication. Limited hypothesis testing will be performed at the 0.05 level, but emphasis will be on estimation. Owing to the focused nature of the design and prespecification of hypotheses, no interim analyses are planned, and no significance 'adjustment' will be applied for multiplicity.

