**Aim-specific Analytic Plan and Power:** **Aim 1** will test the effect of tDCS on dual task costs to standing and walking. The mixed-effects regression approach described above will estimate mean differences between tDCS and sham outcomes at the end of intervention and at three and six months thereafter. We will test the hypothesis that post-intervention changes in outcomes differ between randomized arms, and will additionally estimate timepoint-specific differences between arms in order to assess duration of effects. These models will control for dual-task cost to serial subtraction performance (as a time-varying covariate) to isolate the costs to gait by adjusting for potential differences in task prioritization over time. Sensitivity assessments will stratify by sex to assess empirical evidence of sex-specific effects (see below). Association between model-based estimates of subject-specific intercepts and slopes (generated as random effects) will be examined to assess the degree to which change with time is associated with the average level of function denoted by each measurement. **Sample size estimates:** Prior experiences suggest that 1) inter-individual standard deviation of dual-task costs under either sham or intervention will be no greater than 20%, 2) serial measures of dual task costs express substantial within-participant correlation, in excess of 0.8, and 3) real tDCS intervention reduces dual task costs (Section 3.3.2.2). We assume conservatively that the proposed study will obtain serial correlation of at least 0.75. Assuming evaluable data on at least 57 participants per arm, the trial will provide **90% power to detect a mean difference of 8% between intervention and control arms** in a comparison of dual task costs at any time following cessation of intervention.

The trial will thus be well-powered to detect differences more subtle than the clinically-meaningful differences observed between those with and without a history of falls.  
43-50

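### Aim 1 power uses one SD bound of 20% for both primary outcomes, but the pilot's own sway-speed figure implies an SD of about 38% or 54%

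*Combined protocol and SAP*

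**What the plan says.** Specific Aim 1 (section 2.0) names two primary outcomes: the dual task cost to postural sway speed when standing and to gait speed when walking. The Aim 1 sample size paragraph in section 6.0 treats them as one quantity. On the strength of prior experience, for which it gives no figure, it takes the "inter-individual standard deviation of dual-task costs under either sham or intervention will be no greater than 20" percent. With a serial correlation of 0.75 and 57 evaluable participants per arm, it states "90% power to detect a mean difference of 8% between intervention and control arms". The scope of that claim is any single visit after treatment ends, since it is said to apply "in a comparison of dual task costs at any time following cessation of intervention". It concludes that the trial is "well-powered to detect differences more subtle than the clinically-meaningful differences observed" between people with and without a history of falls.

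Section 1.2 says the pilot trial "enabled more accurate sample size calculations by providing estimates of inter-subject variance in the primary" outcomes and most secondary ones. In the pilot results beside Table 1, "the mean (±SEM) dual task cost to standing balance (i.e., the speed of postural sway) was 50±12" percent at baseline. The pilot had 20 participants, 10 per arm; the n behind the SEM is not stated. For gait-speed cost the text gives p-values but no SD or SEM.

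**The concern.** A standard error of 12 points from a group of 10 or 20 people implies a between-person SD far above 20. The planning bound and the pilot result therefore cannot both be right as printed for sway-speed cost, although the protocol says the pilot informed the variance estimates.

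The power statement has no slack to absorb a larger SD, and it covers a comparison at any single time after the intervention. If the SEM label is correct, a null standing result could be read as evidence against an 8-point effect that the trial had little chance of detecting at a given visit. The plan says that "Limited hypothesis testing will be performed at the 0.05 level, but emphasis will be on estimation", so the practical effect would be confidence intervals for one primary outcome much wider than the sample size section leads a reader to expect.

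**Working it through.** **Inputs.** From section 6.0: two-sided alpha 0.05, 57 per arm, difference 8 points, SD 20, correlation r = 0.75, adjustment for baseline. From section 1.2: SEM 12, pilot n of 10 per arm or 20 in total.

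**Reproducing the plan.** For a baseline-adjusted comparison at one visit, SE = SD × √(1 − r²) × √(2/57).

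- SE = 20 × 0.6614 × 0.1873 = 2.478.
- Power = Φ(8/2.478 − 1.96) = Φ(1.268) = 89.8% (89.3% with a t distribution).

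The stated 90% is reproduced. The largest SD that keeps 90% power for 8 points is 8 / [(1.960 + 1.282) × 0.6614 × 0.1873] = 19.9.

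**SD implied by the pilot.** SD = SEM × √n, with an approximate 95% interval from the chi-square distribution (normality assumed).

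- n = 10: 12 × √10 = 37.9, interval 26.1 to 69.3.
- n = 20: 12 × √20 = 53.7, interval 40.8 to 78.4.

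Conversely, an SD of 20 would give an SEM of 20/√10 = 6.3 or 20/√20 = 4.5. An SEM of 12 fits an SD of 20 or less only if n ≤ (20/12)² = 2.8, that is, two people.

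**Consequences at 57 per arm, r = 0.75.** For the mean of the three follow-ups, assuming compound symmetry, SE = SD × √((1 + 2r)/3 − r²) × √(2/57), where the middle factor is 0.5204. Each cell gives one visit / three-visit mean.

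| SD (source) | SE | Power for 8 points | Detectable at 90% power | 95% CI half-width |
|---|---|---|---|---|
| 20 (plan) | 2.48 / 1.95 | 90% / 98% | 8.0 / 6.3 | 4.9 / 3.8 |
| 26.1 (lower limit, n = 10) | 3.23 / 2.54 | 70% / 88% | 10.5 / 8.2 | 6.3 / 5.0 |
| 37.9 (n = 10) | 4.70 / 3.70 | 40% / 58% | 15.2 / 12.0 | 9.2 / 7.2 |
| 53.7 (n = 20) | 6.65 / 5.23 | 22% / 33% | 21.6 / 17.0 | 13.0 / 10.3 |

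Detectable difference is 3.24 × SE; half-width is 1.96 × SE.

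**Sensitivity to correlation.** At r = 0.8 power for 8 points is 78% / 93% (SD 26.1), 47% / 66% (SD 37.9) and 26% / 39% (SD 53.7). The largest SD that keeps 90% is 19.9 / 25.3 at r = 0.75 and 22.0 / 27.7 at r = 0.8. Single-visit power of 90% would need r of about 0.94 at SD 37.9 or 0.97 at SD 53.7.

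**The case against.** The strongest reply is that everything turns on one label. Table 1, in the same part of the protocol, reports mean ± SD. If the 12 is also an SD, the 20% bound holds and power for 8 points exceeds 99%. The documents cannot settle this, so the loss of power is conditional, although the text as printed says SEM.

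Other points have some force:

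- **Source and population.** The plan credits prior experience generally, and figures missing from the text might show more dispersion. Pilot entry required slow gait and Trail Making B below the 25th percentile, whereas this trial admits an SPPB of nine or below and Trail Making B below 75% of norms. The intervention section nevertheless calls the populations similar, and no other variance figure is printed.
- **Scale.** The plan says that "any necessary transformations (e.g. to combat significant skew) will be performed prior to estimation of mean treatment effects". The 8% and 20% are both on the percent scale, so a transformed analysis would need its own SD and target. Skewness would also make the chi-square intervals less reliable.
- **Repeated measures.** The plan expects more power from using all follow-up, and 57 per arm is its six-month floor. If 65 per arm were available throughout (an assumption), SD 26.1 at r = 0.75 gives 92% for the three-visit mean. Adjustment for serial-subtraction cost might also reduce residual variance. These points help at the favourable edge but do not rescue 37.9 or 53.7, and the claim as worded is about a single time.
- **Range.** Detectable differences of 15.2 and 21.6 rest on the two point estimates only. Over the full SD intervals, the single-visit range is 10.5 to 27.8 (n = 10) or 16.4 to 31.5 (n = 20). Likewise, the half-width exceeds 8 points at the pilot point estimates for one visit, but not at SD 26.1.

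The validity of the treatment estimate and the type I error rate are not affected.

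**Conclusion.** The concern holds. The power arithmetic is correct; the SD input conflicts with the pilot figure for sway-speed cost, and a single power statement cannot serve both outcomes. Taking the SEM label as printed, single-visit power for 8 points is about 40% (n = 10) or 22% (n = 20), rather than 90%. Even the most favourable lower limit, SD 26.1, gives only 70% at r = 0.75 and 78% at r = 0.8. The three-visit mean reaches 90% only near that favourable limit, with r = 0.8 or more participants than the assumed floor.

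This rests on one small baseline estimate, approximate normality for the intervals, compound symmetry for the averages, and a label that only the sponsor can confirm. Nothing in the documents shows 20% to be wrong for gait-speed cost, but nothing printed supports it with a figure either.

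**What to change.** 1. From the pilot data, confirm whether the 12% is an SEM or an SD and the n behind it, compute the SD directly, and reconcile it with the 20% bound.
2. Give a separate, sourced SD for sway-speed cost and for gait-speed cost, noting how the pilot population differs from this one.
3. Restate power or detectable difference for each outcome, at one visit and over all follow-up, and name the analysis scale if a transformation is expected. If the SEM label stands, the point estimates for sway speed are about 15 to 22 points at one visit and 12 to 17 for the three-visit mean at 90% power. Show the uncertainty in the SD alongside them.
4. Keep the 8% claim only for an outcome whose SD supports 20%.
5. For standing, tie the comparison with faller/non-faller differences to the restated detectable difference, and keep it only if the cited differences are larger.

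The cost is a check of existing data and a few rewritten sentences. No extra participants are needed, and the design, estimand and analysis do not change. The stated power for one primary outcome will probably become less favourable.

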## Provide study objectives/aims/hypotheses

---

Our Overall Aim is to compare, in older adults with previous falls, the effects of a *personalized* tDCS intervention designed to target the left dlPFC on the dual task costs to standing and walking, and other physical and cognitive factors that are on the causal pathway to falls and important to everyday function. We will conduct a randomized, sham-controlled, double-blinded trial with assessments at baseline and post-intervention (immediate, 3-, 6-month follow-up) in 144 non-demented men and women (72 per arm) aged 65-85 years who report  $\geq 2$  non-syncopal falls within the previous year and are fearful of falling again, yet have no major neural or musculoskeletal disorders that explain their falls. The tDCS intervention will comprise 20, 20-minute sessions of tDCS over a 4-week period. Importantly, we will utilize current flow modeling from baseline structural MRIs to determine the tDCS electrode placement and stimulation parameters that optimize electrical current flow to the desired target within each participant's brain.

**Specific Aim 1:** To test, in older adult "fallers," the effects of tDCS intervention targeting the left dlPFC on the dual task costs to the control of standing and walking. Standing and walking will be assessed with and without a concurrent cognitive dual task (i.e., verbalized serial subtractions). Primary outcomes will be dual task costs to postural sway speed when standing, and gait speed when walking, as these are well-established measures of functional mobility that are associated with falls.

**Specific Aim 2:** To test, in older adult "fallers," the effects of tDCS intervention targeting the left dlPFC on metrics of physical function that have been linked to frontal executive networks and associated with fall risk. The primary outcome will be the Short Physical Performance Battery (SPPB). Secondary outcomes will include the Timed Up-and-Go (TUG) test of mobility, fear of falling, and habitual physical activity.

**2.0 Specific Aim 3:** To test, in older adult "fallers," the effects of tDCS intervention targeting the left dlPFC on cognitive functions that have been linked to frontal executive networks and associated with fall risk. The primary outcome will be executive function as measured by the Trail Making Test. Secondary outcomes will be derived from tests of processing speed, working memory and sustained attention.

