#### Inclusion criteria:

#### 4.3

1. Aged 65-85 years.
2. Self-report of two or more falls within the past year. Falls will be defined by any event in which the individual unintentionally comes to rest on the ground or other lower level, not as a result of a major intrinsic event (e.g., syncope) or an overwhelmingly external hazard (i.e., car accident).
3. Self-report of fear of falling, as defined by a "yes" answer to the yes-or-no question "Are you worried that you will fall in the future?"
4. At least some mild performance decrement in physical *and* executive function as defined by A) a score of nine or below on the SPPB (range=0-12, 12 reflecting best

performance), and B) a score below the 75% of performance based upon age- and education-based norms in the Trail Making Test (TMT, part B).

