#### Sample size determination

---

*Include power calculations or provide justification for their absence (e.g., pilot/feasibility study).*

Sample size assumptions: For sample size calculations we assume the following: 1) all participants will be included based on their randomized assignment; 2) a two-sided type-I error probability of 0.05; 3) a cumulative attrition rate of at most 15%; 4) modest levels of intervention non-adherence and missing data, such that total missingness at six months post intervention will be at most 20%, leaving 114 participants with evaluable data at the end of follow-up, consistent with our experience in this population; and 5) analyses utilizing multiple imputation will have similar power to those using observed data, consistent with theory and

prior experience. We anticipate greater power in practice owing to data obtained from the multiple follow-up measurements.

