We anticipate greater power attending application of the repeated-measures analysis to all post-intervention data. **Aim 2** will test tDCS effects on physical function as primarily expressed by SPPB. Change scores between 0.5-1.3 have been proposed as the minimum of clinical significance. We will again use the mixed-effects linear model. Based on prior trials and data in this population we expect that SPPB will have baseline standard deviation of 1.5 units and will exhibit high serial correlation over the repeated measurements in this design, as high as 0.9. Assuming a more conservative serial correlation of 0.75, simulation studies (50,000 replicated trials) indicate that the repeated measures design will obtain 92% power to detect a mean intervention-attributable effect on SPPB of 0.5 units. **Aim 3** will test the tDCS effect on executive function measured primarily by the TMT (i.e., TMTB-TMTA); simulation studies similarly indicate that we will achieve at least 90% power to detect standardized effects of the tDCS intervention of 0.35 or greater.

**Missing data:** To accommodate attrition and other sources of missingness, we will utilize the method of multiple imputation by chained equations. At least 50 replicates of each missing value will be generated for inclusion in analyses. This method accommodates clustering of repeated measures at the participant level. We have previously used these methods in trials of anabolic and exercise interventions in similar populations.

Sensitivity analyses: To determine robustness of results we will consider the potential for confounding or effect modification according to baseline age, sex, BMI, and other covariates listed in Section 3.3.7.3. These will be addressed in secondary exploratory and regression analyses in parallel to those described above.

Insurance of scientific rigor—attention to age and sex as biological variables: The trial design is cognizant of the potential influence of age and sex on results. Randomization will be stratified by participant-identified sex classification and this will be acknowledged in all analyses. Sensitivity analyses will also be conducted to address the potential for effect modification by age and these will be reported in publication.

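### Baseline age appears only in sensitivity analyses, and education and the named WTAR adjustor in no stated model; prespecifying them would gain a little precision, best supported for the Trail Making outcome

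*Combined protocol and SAP*

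**What the plan says.** The Overall approach paragraph of the Statistical Plan describes mixed models of the follow-up outcomes that control for the baseline value, and adds: "Analyses will adjust for the stratified design effect (i.e. control for sex"). Sex is the only stratification factor (section 3.1, Study design).

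Two further covariates are named elsewhere:

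- The Aim 1 models also control for the dual-task cost to serial subtraction, as a time-varying covariate (Aim-specific Analytic Plan and Power).
- The WTAR reading score is collected at Visit 1 to adjust changes in executive function (section 5.1). The statistical section does not mention it again.

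On age, the plan acknowledges that "The trial design is cognizant of the potential influence of age and sex on results". Randomisation is stratified by sex, and sex is to be acknowledged in every analysis. Age is examined, as a possible confounder and effect modifier, in sensitivity analyses run beside the main ones, and the age effect-modification results are to be published.

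Inclusion criterion 4B (section 4.3) admits participants on the Trail Making Test part B by "a score below the 75% of performance based upon age- and education-based norms". The Aim 3 outcome is part B minus part A, with no age or education norming stated. Birth date is among the data to be obtained (application form, item 4.5, on HIPAA-covered data), and years of education are recorded at Visit 1.

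**The concern.** The plan treats sex and age unequally. Sex enters every model; age does not, although the protocol itself grades Trail Making performance against age and education. A prognostic variable measured before randomisation can be put into the main model without biasing the comparison. It narrows the interval somewhat and removes most of the effect of a chance difference between arms. Nothing in the allocation scheme balances age across the 65 to 85 entry range.

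The covariate set for Aim 3 is also unfinished: one adjustor is promised in the visit description and absent from the analysis description. At stake are a little precision and a covariate list that is fixed in one place before unblinding.

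**Working it through.** **Inputs from the plan.** "a two-sided type-I error probability of 0.05"; "144 non-demented men and women (72 per arm"); "total missingness at six months post intervention will be at most 20"%; "Assuming evaluable data on at least 57 participants per arm", that is 114 in all. Aim 1: SD 20 points, serial correlation 0.75, difference 8 points, power 90%. Aim 2: SPPB SD 1.5, difference 0.5, power 92%. Aim 3: 0.35 SD, power at least 90%. The documents give no correlation between age and any outcome, so a range is assumed.

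**Step 1: reproduce the stated power without age.** Adjusting one follow-up for baseline multiplies the SD by sqrt(1 − 0.75²) = 0.661.

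- Aim 1: residual SD 20 × 0.661 = 13.23; standard error 13.23 × sqrt(2/57) = 2.478; 8/2.478 = 3.228; 3.228 − 1.960 = 1.268; power 89.8%, against 90% stated. Without baseline adjustment it would be 57.0%.
- Aims 2 and 3: for the mean of three follow-ups under compound symmetry (an assumption), the SD factor is sqrt((1 + 2 × 0.75)/3 − 0.75²) = 0.520. Power is 92.8% for SPPB (92% stated) and 94.8% for Trail Making (at least 90% stated).

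The plan's figures therefore do not depend on age.

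**Step 2: add age.** Suppose age correlates r with the outcome at both baseline and follow-up. The partial correlation given baseline is (r − 0.75r)/sqrt((1 − 0.75²)(1 − r²)). Its square, R², is the share of residual variance that age explains. The equivalent number of extra participants is 114 × (1/(1 − R²) − 1).

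| Assumed r | Partial correlation | R² | Extra participants of 114 | Aim 1 power |
|---|---|---|---|---|
| age not in model | – | – | – | 89.8% |
| 0.2 | 0.077 | 0.6% | 0.7 | 89.9% |
| 0.3 | 0.119 | 1.4% | 1.6 | 90.2% |
| 0.4 | 0.165 | 2.7% | 3.2 | 90.5% |
| 0.5 | 0.218 | 4.8% | 5.7 | 91.1% |

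For the mean of three follow-ups, 1 − 0.75² is replaced by 0.520² = 0.271. R² is then 1.0% (r = 0.2) to 7.7% (r = 0.5), or about 1 to 10 participants. SPPB power rises from 92.8% to between 93.0% and 94.5%, and Trail Making power from 94.8% to between 95.0% and 96.2%.

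**Step 3: chance imbalance in age.** A 1.96-standard-error imbalance at 57 per arm is 1.96 × sqrt(2/57) = 0.367 SD of age. The slope of outcome on age given baseline is (r − 0.75r)/(1 − r²): 0.082 for r = 0.3 and 0.167 for r = 0.5. With the baseline outcome balanced, the shift left in the baseline-adjusted estimate is:

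- dual-task cost: 20 × 0.082 × 0.367 = 0.6 points to 20 × 0.167 × 0.367 = 1.2 points, against a target of 8;
- SPPB: 0.05 to 0.09 units, against 0.5;
- Trail Making: 0.03 to 0.06 SD, against 0.35.

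**Step 4: type I error.** In 10,000 simulated trials per setting (single follow-up, 57 per arm), the rate without and with age was 0.0488 and 0.0475 at r = 0.3, and 0.0476 and 0.0468 at r = 0.5. The Monte Carlo error is about 0.002, so neither model departs materially from 0.05.

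**The case against.** The case for leaving the plan alone is strong in several respects, and most of it stands.

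- **The main models are not limited to baseline outcome and sex.** Aim 1 carries serial-subtraction cost, and WTAR is named for executive function. However, the Aim 1 covariate is measured after randomisation and does not do the work of a baseline prognostic variable, and WTAR never reaches the statistical section.
- **The age analyses are not post hoc.** They are prespecified. Their labels, sensitivity and secondary, also rank the estimates: the main model answers the aim. A reader might infer that two estimates compete on equal terms, but the plan's wording does not support that.
- **The pilot says little about imbalance here.** Its age row reads "Age (years) 83 ± 10 78 ± 10 0.35", and a reader might infer that a 5-year gap is a realistic risk. It came from 10 per arm. If ages in this trial were uniform over 65 to 85 (an assumption), the SD would be 20/sqrt(12) = 5.8 years and the standard error of the arm difference 5.8 × sqrt(2/72) = 0.97 years, so 5 years would be about 5 standard errors.
- **Baseline adjustment already absorbs most of any age effect.** Protection against imbalance is therefore reduced, not lost.
- **The norms concern the Trail Making Test alone.** The documents give no age association for SPPB or dual-task cost.

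What survives is that the improvement is specific and uses data already collected. It also settles the unresolved WTAR statement.

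**Conclusion.** The point holds as a minor improvement. Baseline age is in no stated main model, education in no stated model at all, and the WTAR adjustor is left hanging.

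The expected gain is about 1 to 6 participants of 114 at a single visit, or about 1 to 10 for the average of three visits. Aim 1 power rises by at most about 1.3 percentage points over the range shown. These figures rest on assumed age-outcome correlations of 0.2 to 0.5, equal at baseline and follow-up, and on the plan's 0.75; the three-visit figures also assume compound symmetry. The protocol supports age and education as prognostic for Trail Making only.

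A reader might infer that omitting age biases the comparison, inflates type I error or leaves the trial underpowered. None of these follows: randomisation protects the comparison, the simulated error rate stays near 0.05, and the stated power reproduces without age.

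One limit applies: the plan refers to other sensitivity covariates in a Section 3.3.7.3 that is not in the text available, so that list could not be checked.

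**What to change.** In the Overall approach paragraph, extend the covariate statement so that the main models for all four primary outcomes include the baseline outcome, sex and continuous baseline age. For the part B minus part A model, add years of education and the WTAR score already named at Visit 1. Use the same covariates in the imputation models. Keep arm-by-age as the secondary effect-modification analysis, and fix the list before unblinding.

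The cost is a few lines of text and one degree of freedom for dual-task cost and SPPB, three for Trail Making, out of more than 100. No new data are needed.
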